## 6.6 Study drug preparation and dispensation

The investigator or responsible site personnel must instruct the participant or caregiver to take the study drugs as per protocol. Study drug(s) will be dispensed to the participant by authorized site personnel only. Dose strength and treatment schedule are described in [Table 6-1](#). All dosages prescribed to the participant and all dose changes during the study must be recorded on the Dosage Administration Record CRF.

As per [Section 2.7](#), during a public health emergency as declared by local or regional authorities i.e. pandemic, epidemic or natural disaster, that limits or prevents on-site study visits, delivery of IMP directly to a participant's home may be permitted (if allowed by local or regional health authorities and ethics committees as appropriate) in the event the investigator has decided that an on-site visit by the participant is no longer appropriate or possible, and that it is in the interest of the participant's health to administer the study treatment even without performing an on-site visit. The dispatch of IMP from the site to the participant's home remains under the accountability of the Investigator. Each shipment/provisioning will be for a maximum of 3 months supply. In this case, regular phone calls or virtual contacts (every 4 weeks (+/- 1 week) or more frequently if needed) will occur between the site and the participant for instructional purposes, safety monitoring, drug accountability, investigation of any adverse events, ensuring

participants continue to benefit from treatment and discussion of the participant's health status until the participants can resume visits at the study site.

### **6.6.1 Study drug packaging and labeling**

The study medication packaging has a 2-part label.

In Phase Ib responsible site personnel will add the participant number on the label.

In Phase II, a unique medication number will also be printed on each part of this label which corresponds to one of the treatment arms and a specific visit or dose/dose level. Responsible site personnel will identify the study treatment package(s) to dispense to the participant by using the IRT and obtaining the medication number(s). Site personnel will add the participant number on the label.

Immediately before dispensing the package to the participant, site personnel will detach the outer part of the label from the packaging and affix it to the source document (Drug Label Form) for that participant's unique participant number.

Medication labels will be in the local language and comply with the legal requirements of each country. They will include storage conditions for the drug but no information about the participant. Additionally in Phase II, labels will include the unique medication number.

Nazartinib and capmatinib will be supplied by -Novartis Global Clinical Supply. Nazartinib 25 mg, 50 mg and 100 mg capsules, and 25 mg, 50 mg and 200 mg tablets will be packaged in high-density polyethylene (HDPE) bottles. Capmatinib 100 mg, 150 mg and 200 mg tablets will be packaged in HDPE bottles.

For participants in Phase II Group 5, nazartinib and capmatinib will be supplied by Novartis Global Clinical Supply. Nazartinib 25 mg, 50 mg capsules will be packaged in HDPE bottles. Capmatinib 150 mg and 200 mg tablets will be packaged in HDPE bottles.

### **6.6.2 Drug supply and storage**

Study treatments must be received by designated personnel at the study site, handled and stored safely and properly, and kept in a secured location to which only the investigator and designated site personnel have access. Upon receipt, the study treatment should be stored according to the instructions specified on the drug labels and in the [\[capmatinib Investigator's Brochure\]](#) and [\[nazartinib Investigator's Brochure\]](#) .

### **6.6.3 Study drug compliance and accountability**

#### **6.6.3.1 Study drug compliance**

Compliance will be assessed by the investigator and/or study personnel at each participant visit and information provided by the participant and/or caregiver will be captured in the Drug Accountability Form. This information must be captured in the source document at each participant visit.

### **6.6.3.2 Study drug accountability**

The investigator or designee must maintain an accurate record of the shipment and dispensing of study treatment in a drug accountability log. Drug accountability will be noted by the field monitor during site visits and at the completion of the study. Participants will be asked to return all unused study treatment and packaging on a regular basis, at the end of the study or at the time of study treatment discontinuation.

At study close-out, and, as appropriate during the course of the study, the investigator will return all used and unused study treatment, packaging, drug labels, and a copy of the completed drug accountability log to the Novartis monitor or to the Novartis address provided in the investigator folder at each site.

### **6.6.4 Disposal and destruction**

The study drug supply can be destroyed at the local Novartis facility, Drug Supply group or third party, as appropriate.

Study treatment destruction at the investigational site will only be permitted if authorized by Novartis in a prior agreement and permitted by local regulations.

## **7 Visit schedule and assessments**

### **7.1 Study flow and visit schedule**

Table 7-1 and Table 7-2 lists all of the assessments and indicates with an “X”, the visits when they are performed. All data obtained from these assessments must be supported in the participant’s source documentation.

No CRF will be used as a source document.

Screening/baseline evaluations (including baseline radiological assessments) must be performed  $\leq$  28 days of Cycle 1 Day 1. Laboratory assessments performed as part of the screening evaluations and within 72 hours of the first dose of study treatment, are not required to be repeated on the first dosing day.

During the course of the study visits, test and/or procedures should occur on schedule whenever possible. During the Phase Ib part of the study, for C2D1, a visit window of +3 days is permitted to ensure minimal follow-up of 28 days during cycle 1. For all other visits, a visit window of +/- 3 days is allowed. HBV/HCV results should be available prior to first dose of study treatment (capmatinib + nazartinib). On PK collection days of Cycle 1, the window is only +/- 1 day. PK samples of Cycle 1 Day 1 must be collected at the same day of first dose.

Radiological assessments must be performed +/-7 days of the scheduled date of the assessment.

As per [Section 2.7](#), during a public health emergency as declared by local or regional authorities i.e., pandemic, epidemic or natural disaster, that limits or prevents on-site study visits, alternative methods of providing continuing care may be implemented by the investigator as the situation dictates. If allowed by local health authority and depending on operational capabilities, phone calls, virtual contacts (e.g., tele consult) or visits by site staff/ home nursing staff to the participant's home, can replace on-site study visits, for the duration of the disruption until it is safe for the participant to visit the site again.

**Table 7-1 Visit evaluation schedule for Phase Ib and Phase II Groups 1 to 4**

	Category	Protocol Section	Screening Phase		Treatment Phase													Follow-Up			
			Molecular Pre-screening	Screening	Cycle 1					Cycle 2					Subsequent cycles			EoT	30-day Safety F/U	Disease progression F/U	Survival F/U every 3 months
Day of Cycle				-28 to 1	1	2	8	15	16	22	1	2	8	15	22	1	15				
Obtain Molecular Pre-screening Informed Consent	D	7.1.1.	X																		
Obtain Main Informed Consent	D	7.1.2.		X																	
IRT Registration (Phase II)		6.5.1.	X	X														X			
Participant history																					
Demography	D	7.1.2.2.	X	X																	
Inclusion/exclusion criteria	D		X	X																	
Current medical conditions	D	7.1.2.2.		X																	
Diagnosis and extent of cancer	D	7.1.2.2.		X																	
Prior antineoplastic therapies	D	7.1.2.2.		X																	
Smoking history	D	7.1.2.2.		X																	
Prior/concomitant medications	D	7.1.2.2.			Continuously													X			
Antineoplastic therapies since discontinuation of study treatment	D	7.1.2.2.																	X	X	X
Physical examination	S	7.2.2.1.		X	X	X	X		X	X	X	X	X	X	X			X			
Vital signs	D	7.2.2.2.		X	X	X	X		X	X	X	X	X	X	X			X			
Height	D	7.2.2.3.		X																	
Weight	D	7.2.2.3.		X	X						X					X		X			
Performance status	D	7.2.2.4.		X	X						X					X		X			

	Category	Protocol Section	Screening Phase		Treatment Phase													Follow-Up				
			Molecular Pre-screening	Screening	Cycle 1					Cycle 2					Subsequent cycles			EoT	30-day Safety F/U	Disease progression E/IL	Survival F/U every 3 months	
Day of Cycle				-28 to 1	1	2	8	15	16	22	1	2	8	15	22	1	15					
Laboratory Assessments																						
Hematology	D	7.2.2.5.1.		X	X		X	X		X	X		X	X	X	X	X	X up to Cycle 6 only	X			
Chemistry	D	7.2.2.5.2.		X	X		X	X		X	X		X	X	X	X	X	X up to Cycle 6 only	X			
Coagulation	D	7.2.2.5.3.		X																		
Urinalysis	D	7.2.2.5.4.		X	X														X			
HBV testing	D	6.3.2. 7.2.2.5.5.		X	In cases of positive HBV testing, monitor HBV-DNA every 4 weeks or every 12 weeks, per Table 6-10 and Table 6-11 (or more frequently if clinically indicated).																	
HCV testing	D	6.3.2. 7.2.2.5.5.		X	In cases of positive HCV-Ab, monitor HCV-RNA every 8 weeks, per Table 6-12 (or more frequently if clinically indicated).																	
Pregnancy test	D	7.2.2.5.6.		X	X						X					X			X			

	Category	Protocol Section	Screening Phase		Treatment Phase												Follow-Up				
			Molecular Pre-screening	Screening	Cycle 1						Cycle 2						Subsequent cycles	EoT	30-day Safety F/U	Disease progression E/I/LL	Survival F/U every 3 months
Day of Cycle				-28 to 1	1	2	8	15	16	22	1	2	8	15	22	1	15				
Imaging																					
Tumor evaluation as per RECIST 1.1 CT/MRI: - Mandatory at each evaluation: chest, abdomen - Mandatory if lesions at baseline: brain, skin - If clinically indicated: bone, other tumor sites	D	7.2.1.		X												X Every 8 wks (12 wks from C13D1)		X (if not conducted within 30 days of EOT)		X every 8 wks	
ECG (triplicate)	D	7.2.2.6.1.		X	X						X					X		X			
Safety																					
AEs	D	8.	X Procedural SAE only	X	Continuously																
Biomarkers																					
Molecular Pre-Screening (Tumor sample archival or newly obtained)		7.1.1. 7.2.4.	X																		
Whole Blood sample for determination of MET and EGFR status in cfDNA		7.2.4.		X*												X C3 and every third cycle		X			

	Category	Protocol Section	Screening Phase		Treatment Phase												Follow-Up						
			Molecular Pre-screening	Screening	Cycle 1						Cycle 2						Subsequent cycles	EoT	30-day Safety F/U	Disease progression E/IL	Survival F/U every 3 months		
Day of Cycle				-28 to 1	1	2	8	15	16	22	1	2	8	15	22	1	15						
Study Drug administration	D	6.1.1.			Continuously																		
PK sampling (Phase Ib part)	D	7.2.3.2.			X	X	X	X	X		X	X				X	C3 and 4 only						
PK sampling (Phase II part)	D	7.2.3.3.			X	X	X				X	X				X	C3 and 4 only						
Meal Recorded (Full PK participants)		6.1.1.			X						X												
Survival contact (telephone call)		7.1.6.																	X				
* Collect during screening phase or at C1D1 before the first dose of study drugs is administered.																							

Period	Category	Protocol Section	Screening		Treatment – Capmatinib Monotherapy			Extension Treatment (ET) – Capmatinib + Nazartinib combination therapy			Follow-up		
			Molecular pre-screening	Screening	Cycle 1	Cycle 2 and beyond	EOT	ET-Cycle 1	ET-Cycle 2 and beyond	ET-EOT	30-day Safety F/U	Post-treatment F/U	
Day of cycle			-	-28 to -1	1	1	-	1	1	-	-	-	
Performance Status (ECOG)	D	7.2.2.4.		X	X	X	X	X	X	X			
Hematology	D	7.2.2.5.1		X	X	X up to Cycle 6 only	X	X	X up to ET-Cycle 6 only	X			
Chemistry	D	7.2.2.5.2.		X	X	X up to Cycle 6 only	X	X	X up to ET-Cycle 6 only	X			
Coagulation	D	7.2.2.5.3.		X (≤72 hr before C1D1)	As clinically indicated								
Urinalysis (dipstick)	D	7.2.2.5.4.		X	As clinically indicated								
HBV testing	D	6.3.2. 7.2.2.5.5.		X					In cases of positive HBV testing, monitor HBV-DNA every 4 weeks, per Table 6-10 and Table 6-11 (or more frequently if				

Period	Category	Protocol Section	Screening		Treatment – Capmatinib Monotherapy			Extension Treatment (ET) – Capmatinib + Nazartinib combination therapy			Follow-up	
			Molecular pre-screening	Screening	Cycle 1	Cycle 2 and beyond	EOT	ET-Cycle 1	ET-Cycle 2 and beyond	ET-EOT	30-day Safety F/U	Post-treatment F/U
Day of cycle			-	-28 to -1	1	1	-	1	1	-	-	-
								clinically indicated).				
HCV testing		6.3.2. 7.2.2.5.5.		X				In cases of positive HCV-Ab, monitor HCV-RNA every 4 weeks, per Table 6-12 (or more frequently if clinically indicated).				
Pregnancy Test (Serum)	D	7.2.2.5.6.		X (≤72 hr before C1D1)			X			X		
Pregnancy Test (Urine)	D	7.2.2.5.6.				X			X			
Tumor evaluation	D	7.2.1.		X		Cycle 3 then every 8 weeks (from cycle 13 every 12 weeks)	X (Not required if previous assessment was performed ≤28 days)	X 	ET-Cycle 3 then every 8 weeks (from cycle 13 every	X (Not required if previous assessment was performed ≤28 days)		X every 8 weeks

Period	Category	Protocol Section	Screening		Treatment – Capmatinib Monotherapy			Extension Treatment (ET) – Capmatinib + Nazartinib combination therapy			Follow-up	
			Molecular pre-screening	Screening	Cycle 1	Cycle 2 and beyond	EOT	ET-Cycle 1	ET-Cycle 2 and beyond	ET-EOT	30-day Safety F/U	Post-treatment F/U
Day of cycle			-	-28 to -1	1	1	-	1	1	-	-	-

X Assessment to be recorded in the clinical database or received electronically from a vendor  
S Assessment to be recorded in the source documentation only  
1 Can be collected up to C1D1  
2 Each participant must sign separate combination treatment ICF prior to any assessments of the Extension Treatment period or first dose with combination therapy  
3 Not required if the EOT scan is within 28 days of ET-C1D1, then the EOT scan can be defined as re-baseline of extension. Otherwise, a re-baseline scan should be arranged 28 days prior to ET-C1D1. In case exceed 28 days of C1D1 and no re-scan was done, the EOT scan can be used as re-baseline for efficacy assessment

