[Part 2 of 2 of the document. The other parts are not shown.]

1. All participants must be screened with HBV serologic markers: HBsAg, HBsAb, and HBcAb.
2. If HBsAg and/or HBcAb are positive, test for HBV-DNA.
3. Refer to [Table 6-10](#) for actions to be taken based on screening HBV results.
4. If a participant is HBsAg positive or HBV-DNA positive BUT is not on antiviral therapy:
  - a. Consult a physician with expertise in managing HBV
  - b. Initiate antiviral therapy with entecavir 0.5 mg q.d. 1-2 weeks prior to first dose of study treatment (capmatinib + nazartinib). Note: ongoing participants prior to initiation of Amendment 3 follow the Urgent Safety Measure.
  - c. If a participant cannot take entecavir or if entecavir is not available at your institution, contact Novartis to select an appropriate antiviral therapy.
  - d. If antiviral therapy cannot be given, the participant is not eligible for study treatment (capmatinib + nazartinib).
  - e. During the study, monitor HBV-DNA every 4 weeks (or more frequently if clinically indicated). (Refer to [Table 6-11](#) if there is evidence of viral reactivation on study)
  - f. Antiviral therapy should continue for at least 4 weeks after the last dose of study treatment (capmatinib + nazartinib).
5. Participants who are HBsAg positive or HBV-DNA positive at screening and already have been receiving antiviral therapy are eligible provided the participant remains on antiviral treatment.
  - a. Identify a consulting physician with expertise in managing HBV who can provide treatment guidance, if required, while the participant is on study.
  - b. HBV-DNA should be monitored every 4 weeks (or more frequently if clinically indicated).
  - c. Antiviral therapy should continue for at least 4 weeks after the last dose of study treatment (capmatinib + nazartinib).
6. Refer to [Table 6-11](#) for guidelines of management for HBV reactivation.

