**Table 6-10 Actions to be taken based on hepatitis B results screening**

Test	Result	Result	Result	Result	Result
HBV-DNA	+	+ or -	-	-	-
HBsAg	+ or -	+	-	-	-
HBsAb	+ or -	+ or -	+ and no prior HBV vaccination	- or + with prior HBV vaccination	- or + with prior HBV vaccination
HBcAb	+ or -	+ or -	+ or -	+	-
Required actions	
* Consult a physician with expertise in managing HBV. After the consultation, antiviral therapy should be started 1-2 weeks prior to first dose of study treatment (capmatinib + nazartinib). Recommended antiviral therapy is entecavir 0.5 mg q.d. Contact Novartis if a participant cannot take entecavir or if entecavir is not available at your institution. Monitor HBV-DNA every 4 weeks (or more frequently if clinically indicated). Antiviral therapy should continue for at least 4 weeks after the last dose of study treatment (capmatinib + nazartinib).
		
No antiviral therapy. Monitor HBV-DNA every 4 weeks.
		
No antiviral therapy. HBV-DNA screening not required unless if HBsAg and/or HBcAb are positive

*Recommended antiviral therapy is entecavir 0.5 mg q.d. Contact Novartis if a participant cannot take entecavir or if entecavir is not available at your institution. Antiviral therapy should continue for at least 4 weeks after the last dose of study treatment (capmatinib + nazartinib).
					

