### Screening for hepatitis C

Screen all participants for HC Ab. If HC Ab is detected then check HCV-RNA. Only participants who are HC Ab negative or HC Ab positive with an undetectable level of RNA are eligible to be enrolled. Note: participants with detectable HCV-RNA will not be eligible for the study. Participants with HCV-Ab positive or history of hepatitis C infection should be monitored every 8 weeks (or more frequently if clinically indicated) with HCV-RNA.

All screening evaluations will be performed within 28 days prior to Treatment Day 1. HBV/HCV tests will be performed by a local laboratory for the Phase Ib part and by a central laboratory for the Phase II part. HBV/HCV test results should be available prior to the first dose of study treatment (capmatinib + nazartinib). Participants with positive baseline hepatitis B results have to start antiviral treatment 1 to 2 weeks prior to the first dose of study treatment (capmatinib + nazartinib) and need to be monitored with HBV-DNA every 4 weeks (or more frequently if clinically indicated). Participants with HC Ab positive or history of hepatitis C infection should be monitored every 8 weeks (or more frequently if clinically indicated) with HCV-RNA.

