#### 7.2.2.5.5 HBV and HCV testing

HBV tests outlined in [Table 7-5](#) will be performed as per the assessment schedule in [Table 7-1](#) and [Table 7-2](#).

HCV tests outlined in [Table 7-5](#) will be performed as per the assessment schedule in [Table 7-1](#) and [Table 7-2](#).

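### Group 5: Table 7-2 schedules HBV-DNA monitoring of marker-positive participants only in the extension, so the combination can be started on a screening result 8-12 weeks old or older

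*Protocol*

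**What the plan says.** - **Table 7-2 (Group 5), HBV testing row.** There is an X at screening. Monotherapy Cycle 1, Cycle 2 and beyond, and EOT are blank. The text "In cases of positive HBV testing, monitor HBV-DNA every 4 weeks, per" Tables 6-10 and 6-11 sits under the extension columns.
- **Status of the table.** Section 7.1 states that "Table 7-1 and Table 7-2 lists all of the assessments and indicates with an" X when each is done. Section 7.2.2.5.5 adds that HBV tests "will be performed as per the assessment schedule in" those two tables.
- **Table 6-10.** For participants negative for HBsAg and HBV-DNA who are HBcAb-positive, or HBsAb-positive without prior vaccination, the action is "No antiviral therapy. Monitor HBV-DNA every 4 weeks". No group or treatment period is named.
- **Section 6.3.2, item 4.** For participants positive for HBsAg or HBV-DNA and not on antivirals: "Initiate antiviral therapy with entecavir 0.5 mg q.d. 1-2 weeks prior to first dose of study treatment (capmatinib + nazartinib", then "During the study, monitor HBV-DNA every 4 weeks (or more frequently if clinically indicated".
- **Section 7.1.2.** Participants with positive baseline hepatitis B results must start antivirals and "need to be monitored with HBV-DNA every 4 weeks (or more frequently if clinically indicated".
- **Section 7.1.** "HBV/HCV results should be available prior to first dose of study treatment (capmatinib + nazartinib". No age limit or re-test is attached to that requirement.
- **Table 6-11.** New measurable HBV-DNA in a participant negative for HBV-DNA and HBsAg at screening is reactivation. The combination is interrupted, a specialist consulted, antivirals started and an SAE recorded.

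**The concern.** Group 5 is the only group in which the combination is not the first treatment given. The HBV safeguards are built around a screening test shortly before the first combination dose. In Group 5 a whole period of monotherapy lies between the two, and Table 7-2 leaves it without a scheduled HBV-DNA test, while Table 6-10 tells sites to test the relevant participants every 4 weeks. Two sites could act differently and each point to the protocol.

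The participant at risk is HBsAg-negative and HBV-DNA-negative at screening but marker-positive. This participant gets no antiviral and relies on monitoring alone. If viraemia appears during monotherapy and is not looked for, the combination may be started on top of it. There is also a cost to interpretation. The footnote to Table 6-11 dates a reactivation by the laboratory result that defines it, so viraemia that arose on monotherapy but was found in the extension is dated to, and counted in, the combination on-treatment period of Section 10.7.1.1.

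**Working it through.** The plan gives no figure for the age of the HBV-DNA result at the start of the combination, so it is derived from the schedule.

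**Inputs**
- Group 5 screening runs from Day -28 to Day -1 (Table 7-2).
- A cycle is 28 days (Section 7.1.3), so C2D1 is Day 29 and C3D1 is Day 57.
- The first on-treatment scan is at Cycle 3 (Table 7-2), with a window of ±7 days (Section 7.2.1).

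**Formula.** For a screening test on Day -k and a date of interest Day D, with C1D1 as Day 1, age of result = (D - 1) + k, where k runs from 1 to 28.

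**Results under Table 7-2 as printed**
- Nominal first scan, D = 57: 56 + 1 = 57 to 56 + 28 = 84 days, about 8 to 12 weeks.
- With the scan window: D = 50, k = 1 gives 50 days; D = 64, k = 28 gives 91 days.
- If ET-C1D1 follows that latest scan by 28 days: 91 + 28 = 119 days. This is an illustration, not a maximum. Progression may come later, and footnote 3 of Table 7-2 allows for gaps beyond 28 days.
- After six monotherapy cycles, D = 169: 168 + 1 = 169 to 168 + 28 = 196 days, about 24 to 28 weeks.

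**Tests not scheduled.** At 4-weekly intervals, two draws (C2D1 and C3D1) would fall by the first scan and six by the end of six cycles. Table 7-2 schedules none of them.

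**Comparison with Groups 1 to 4.** Their combination starts on C1D1 and screening falls within 28 days of it, so their result is at most 28 days old. With 4-weekly testing in Group 5, the C2D1 result would be 57 - 29 = 28 days old at C3D1.

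**Other safeguards.** The ALT rule in Section 6.3.2 needs ALT above 5 x ULN (8 x ULN if baseline was above 3 x ULN). Its immediate HBV-DNA re-test is for participants already under HBV-DNA monitoring, which under Table 7-2 arguably does not include Group 5 on monotherapy. The viral panel required for everyone else contains no HBV-DNA. Scheduled chemistry in Table 7-2 is marked up to Cycle 6 only.

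**How many participants.** The documents give no marker prevalence and no viraemia rate on capmatinib. At an assumed HBcAb prevalence of 5-30%, 0.05 x 30 = 1.5 to 0.30 x 30 = 9 of 30 participants are HBcAb-positive. This is only an order of magnitude. The monitoring columns also include unvaccinated HBsAb-positive participants, some HBcAb-positive participants fall in the antiviral columns instead, and only those who enter the extension meet the risk.

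**The case against.** The strongest reply is that the HBV rules are about the combination. Sections 6.3.2, 7.1 and 7.1.2 and Tables 6-10 and 6-11 repeatedly gloss study treatment as capmatinib + nazartinib, which Group 5 receives only in the extension. On that view Table 7-2 is deliberate. The HCV row is placed the same way, whereas the coagulation and urinalysis instructions begin under monotherapy. Table 7-1 does not contradict this, because Groups 1 to 4 take the combination from Cycle 1. This stands as an arguable reading. It does not close the gap: if the rules exist to protect participants on the combination, HBV status should be current when the combination starts, and Section 7.1 is satisfied by the old screening result.

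Two stronger readings are tempting and should not be drawn.
- A reader might infer that Table 7-2 contradicts Section 6.3.2 item 4e and Section 7.1.2 for the participant at risk. Both of those texts concern participants positive at screening who must take antivirals. For the untreated, marker-positive participant only the Table 6-10 cell applies.
- A reader might infer that the plan already requires the 1-2 week antiviral lead-in here and that Table 7-2 causes it to be missed. The lead-in is tied to screening or baseline positives. Viraemia that appears later falls under Table 6-11, which has no lead-in and whose actions name only the combination.

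**Conclusion.** The point holds in a limited form. For Group 5, Table 7-2 and Table 6-10 give different instructions for marker-positive participants without HBsAg or HBV-DNA, and nothing in the text shown requires a fresh HBV-DNA result before ET-C1D1. The result relied on is about 8-12 weeks old if progression is found at the first scan and older otherwise, against at most 28 days in Groups 1 to 4. The consequence is possible undetected viraemia at the first combination dose. How often this would occur cannot be estimated from the documents.

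This is a patient-safety correction worth making. It does not affect the primary ORR analysis. It assumes progression at a scheduled scan followed by a prompt switch, and column positions read from an extracted table; the HBV and HCV rows agree on the extension. Part 1 of the protocol, including any extension-entry criteria, and the opening of Section 6.3.2 are not shown and could narrow the point.

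**What to change.** In Table 7-2, schedule HBV-DNA every 4 weeks for the marker-positive participants in the monitoring columns of Table 6-10, at the existing monotherapy Day 1 visits and at EOT. At minimum, require an HBV-DNA result from within 28 days before ET-C1D1, reviewed before the first combination dose.

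If that result is newly positive, consult a physician experienced in HBV and start antiviral therapy 1-2 weeks before ET-C1D1, mirroring what Table 6-10 does for screening positives. Say so in Table 6-10 or 6-11, since neither now tells a site what to do about viraemia found on monotherapy.

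The cost is a few extra assays at visits that already take place, in marker-positive participants only, plus a change to one table row and its cross-references. The combination may be delayed by 1-2 weeks for anyone newly positive at the last draw. A positive found at C2D1 leaves 28 days before the nominal C3D1 scan, enough for the lead-in without delay.
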